15.0 REFERENCES20

1.0 INTRODUCTION

This document provides a detailed description of the statistical methods and procedures to be implemented during the analysis of Acerus Pharmaceutical Corporation protocol # NAT-2016-01. The proposed methods and approaches to the data analysis should be viewed as flexible if the data suggest and warrant deviations from this plan. However, any deviations from this analysis plan must be substantiated by sound statistical rationale and documented in the final clinical study report.

2.0 STUDY OBJECTIVES

2.1 Primary Objective

The primary objective of the study is to measure patient satisfaction with testosterone replacement therapy before (for non-naïve patients), during and after treatment with Natesto™.

2.2 Secondary Objectives

The secondary objectives of this study are to evaluate the following:

1. Improvement in hypogonadism symptoms
2. Patient treatment preference versus prior testosterone replacement therapy
3. Frequency of daily dose of Natesto™
4. Safety monitoring

2.3 Exploratory Objectives

Exploratory objectives will include analysis of the rate of change of the primary or secondary efficacy measures over the treatment period be that 90 days for patients on Natesto™ BID or 120 days for patients on Natesto™ TID.

3.0 STUDY OVERVIEW

This is a phase 4, multi-centre study consisting of two study periods and a post study follow-up.

90-Day Treatment Period: With potential extension by 30 days for those patients requiring a dose increase, as determined by the treating physician. Participants receiving 122.5mg of Natesto™ (5.5 mg of testosterone) per nostril twice daily may have an increased daily dose adjustment on Day 90, based on their hypogonadism symptoms.

1-Day Study Completion Period: Patient will return to the site for examination, discussion of symptoms with physician and questionnaire completion. Serum testosterone levels will be determined for all patients on Day 90 (BID dose) and on Day 120 for the TID patients.

Post Study Follow-Up: All study patients will be followed up at Day 150 after the Treatment Phase to determine if they have continued using NATESTO and why (or why not?).

Schedule of Procedures

Study Phase	Treatment Period						
	Treatment Start	Efficacy Analysis				Post Study Follow Up	Early Withdrawal/Termination
	Day 0	Day 30 +/- 3 days	Day 60 +/- 3 days	End of Study: BID Patients Day 90 +/- 3 days	End of Study: TID Patients Day 120 +/- 3 days	Day 150 +/- 3 days	
Visit	1	2	3	4 ^a	5 ^b	6	
Location/Type	clinic	telephone	telephone	clinic	clinic	telephone	clinic
Study Procedures:							
Inclusion/exclusion criteria	X						
Informed consent	X						
Medical history	X			X	X		
Demographics	X						
Physical examination + nasal exam	X			X	X		X
Height and weight	X			X	X		X
Vital signs (HR, BP, RR, and temperature)	X			X	X		X
Serum total testosterone plus safety labs	X ^c			X	X ^d		X
Participant training on NATESTO administration	X						
Provide Study Drug Access Card for NATESTO	X						
Provide Pharmacy Prescription	X			X ^g			
Potential study drug daily dose increase to TID				X			
TSQM	X ^e	X	X	X	X		X
qADAM	X ^f	X	X	X	X		X
Patient Preference + Use	X			X	X		X
Concomitant medications	X	X	X	X	X		X
Assess adverse events	X	X	X	X	X		X
Assess voluntary treatment continuation						X	

- a. All patients are required to complete Visit 4
- b. Only patients assigned to NATESTO TID are required to complete Visit 5
- c. Naïve patients will require confirmation of hypogonadism by serum testosterone within the last 6 months
- d. Only patients who continued on TID
- e. TSQM to be completed by non-naïve patients only
- f. qADAM to be completed by all patients
- g. Patients who are assigned to NATESTO TID will be provided with a new Pharmacy Prescription increasing their dosage to TID

4.0 SAMPLE SIZE

A sample size of approximately 100 participants will be selected to provide a sufficient number of participants for the analysis. Since this is an observational study, no formal sample size calculation will be performed. Interim analysis and sample size re-estimation may be performed after results are acquired from 50 and 75 patients.

5.0 ANALYSIS ENDPOINTS

5.1 Primary Efficacy Endpoints

Primary efficacy is the self-reported patient satisfaction with treatment assessed by the Treatment Satisfaction Questionnaire for Medication (TSQM), a validated, 9-item instrument with domains for Effectiveness, Convenience and Global Satisfaction.

The primary efficacy endpoints are:

- change in satisfaction for each TSQM domain from Visit 1 (Day 0) to Visit 4 (Day 90) for non-naïve BID patients
- change in satisfaction for each TSQM domain from Visit 1 (Day 0) to Visit 5 (Day 120) for non-naïve TID patients

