7.0 DATA CONVENTIONS

7.1 Definitions

Visit 1 (Day 0) is defined as the day in which the patient provides informed consent and starts the study. All study days are determined relative to Visit 1 (Day 0).

End of treatment is defined as the day on which the last dose of treatment is taken. This date was not collected for this study.

End of study is defined as the last day on which data were collected from the patient. Using the Early Termination Visit eCRF, it is the date of early termination. Using the Visit 6 - Post Study Follow-Up (Day 150) eCRF, it is the post study follow-up date. Otherwise, it is the date of last contact, if the patient was lost to follow-up, or the date of death, if the patient died.

Baseline serum testosterone values will be defined as those values recorded on Visit 1 (Day 0). Naive patients were asked for 2 measurements (average used in analysis) and non-naive patients were asked for 1 measurement at Baseline (Visit 1/Day 0).

Serum Testosterone will be reported in (nmol/L). If value is reported in (ng/dL) then value will be multiplied by 0.0347 to convert to (nmol/L).

Testosterone collected in (pmol/L) will be considered Free Testosterone and will not be used in any analyses.

Hematocrit will be reported in (%). Values will be multiplied by 1 and if the value is less than 1 then the value will be multiplied by 100.

Total Cholesterol will be reported in (mmol/L). If value is reported in (mg/dL) then value will be divided by 38.67 to convert to (mmol/L).

LDL will be reported in (mmol/L). If value is reported in (mg/dL) then value will be divided by 38.67 to convert to (mmol/L).

HDL will be reported in (mmol/L). If value is reported in (mg/dL) then value will be divided by 38.67 to convert to (mmol/L).

Triglycerides will be reported in (mmol/L). If value is reported in (mg/dL) then value will be divided by 88.57 to convert to (mmol/L).

Hemoglobin will be reported in (g/L). If value is reported in (g/dL) then value will be divided by 0.1 to convert to (g/L).

ALT and AST will be reported in (U/L).

Study duration (days) will be defined as the (end of study date – date of informed consent + 1).

The ALL treatment group will be defined as patients who were either naïve or non-naïve.

The BID treatment group will be defined as patients who were either naïve or non-naïve and did not titrate to TID (Visit 5/Day 120).

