The TID treatment group will be defined as patients who were either naïve or non-naïve and did titrate up to TID (Visit 5/Day 120).

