9.0 EFFICACY ANALYSES

9.1 Primary Efficacy Analyses

The primary efficacy analyses will be performed using the ITT and the respective PP populations.

BID Treatment Group:

TSQM domain scores at Visit 1, Visit 2, Visit 3 and Visit 4 will be summarized and presented descriptively for non-naïve patients. There are three domains which include effectiveness (3 items), convenience (3 items) and global satisfaction (3 items).

TSQM domain change from baseline (Visit 1) scores at Visit 2, Visit 3 and Visit 4 (primary endpoint) will be summarized and presented descriptively for non-naïve patients using 2 different approaches, LOCF and no LOCF. Change from baseline scores will be analysed using a two-sided paired t-test or a non-parametric equivalent if warranted by the data.

TID Treatment Group:

TSQM domain scores at Visit 1, Visit 2, Visit 3, Visit 4 and Visit 5 will be summarized and presented descriptively for non-naïve patients. There are three domains which include effectiveness (3 items), convenience (3 items) and global satisfaction (3 items).

TSQM domain change from baseline (Visit 1) scores at Visit 2, Visit 3, Visit 4 and Visit 5 (primary endpoint) will be summarized and presented descriptively for non-naïve patients using 2 different approaches, LOCF and no LOCF. Change from baseline scores will be analysed using a two-sided paired t-test or a non-parametric equivalent if warranted by the data.

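### Both primary TSQM endpoints are confined to groups formed by the Day 90 dose decision; the undivided Day 90 change in non-naïve patients is only an exploratory row

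*SAP*

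**What the plan says.** Section 2.1 makes the primary objective patient satisfaction before, during and after treatment, with no split by later dose.

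Section 3.0 says that patients on the twice-daily dose "may have an increased daily dose adjustment on Day 90, based on their hypogonadism symptoms", and describes the 30-day extension as being for "those patients requiring a dose increase, as determined by the treating physician". Section 7.1 then defines BID as patients who did not titrate and TID as those who did.

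Section 5.1 gives two primary endpoints: "change in satisfaction for each TSQM domain from Visit 1 (Day 0) to Visit 4 (Day 90) for non-naïve BID patients", and the matching Day 120 change for non-naïve TID patients. Section 9.1 tests them under separate BID and TID headings and states: "The primary efficacy analyses will be performed using the ITT and the respective PP populations". The TID block there also reports the Visit 4 change.

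The ALL-patient endpoints are set at Visit 5: TSQM in Section 5.4 (exploratory) and total qADAM in Section 5.2 (secondary). The schedule footnotes in Section 3.0 read "All patients are required to complete Visit 4" and "Only patients assigned to NATESTO TID are required to complete Visit 5". The undivided Visit 4 TSQM change appears only as one visit within the exploratory ALL-group analysis of Section 9.3.

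**The concern.** For patients who reach Day 90, group membership is settled by a judgement about symptoms at the visit where the BID primary endpoint is measured. Symptoms are plausibly related to satisfaction, above all in the Effectiveness and Global Satisfaction domains. Patients doing poorly tend to leave the BID group, and those who remain look better than the whole.

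No primary or secondary TSQM endpoint covers the undivided non-naïve group. The named ALL-patient endpoints do not fill the gap. Only TID patients must attend Visit 5, so without LOCF those endpoints are essentially TID results; with LOCF they mix Day 90 and Day 120 values.

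What is at stake is interpretation. The BID Day 90 result could be taken as the change in satisfaction among all non-naïve patients who used the product, which it is not.

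**Working it through.** The SAP gives no effect size, SD, number of non-naïve patients, titration share or correlation, so there is no planned figure to reproduce. It does give the test (paired t-test, two-sided 0.05, unadjusted; Sections 8.0 and 9.1) and a total of about 100 participants (Section 4.0).

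**Assumptions.** N = 50 non-naïve patients; the 30% with the worst Day 90 symptom index titrate (15 TID, 35 BID); TSQM change has mean 0 and SD 1; its correlation with the symptom index, scored so that higher is better, is ρ; no dropout.

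**Closed form, strict cut-off.** With p = 0.30, z = −0.524 and φ(z) = 0.348:
- BID mean = ρφ(z)/(1−p) = 0.497ρ, i.e. 0.149, 0.248 and 0.348 at ρ = 0.3, 0.5 and 0.7.
- TID Day 90 mean = −ρφ(z)/p = −1.159ρ, i.e. −0.579 at ρ = 0.5.
- Undivided mean at ρ = 0.5 = 0.7 × 0.248 − 0.3 × 0.579 = 0.00.

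If the physician's judgement adds noise with the same SD as the symptom index, ρ is divided by √2: at ρ = 0.3, 0.497 × 0.212 = 0.105.

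**Simulation** (40,000 trials per row; upward rejections by the two-sided 0.05 test):

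| ρ | Decision | BID mean (SD) | BID rejects upward | Undivided Day 90 rejects upward |
|---|---|---|---|---|
| 0.1 | noisy / strict | +0.03 / +0.05 | 3.9% / 4.6% | 2.5% / 2.5% |
| 0.3 | noisy / strict | +0.10 / +0.15 | 9.0% / 14.0% | 2.5% / 2.5% |
| 0.5 | noisy / strict | +0.17 / +0.24 | 17.8% / 33.1% | 2.5% / 2.3% |
| 0.7 | noisy / strict | +0.24 / +0.34 | 31.9% / 61.2% | 2.5% / 2.5% |

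**Dropout.** Suppose the leavers are those with low Day 30 change (selected with noise, Day 30 to Day 90 correlation 0.7). Section 7.1 counts them as BID, because they did not titrate. Ranges run from ρ = 0.3 noisy to ρ = 0.7 strict:

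| Leavers | BID, observed | BID, LOCF | Undivided Day 90, observed | Undivided Day 90, LOCF |
|---|---|---|---|---|
| 10% | +0.19 to +0.43 | 0.00 to +0.20 | +0.09 | −0.04 |
| 20% | +0.26 to +0.48 | −0.06 to +0.10 | +0.17 | −0.06 |

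Among observed patients the BID minus undivided gap, which isolates selection by titration, is +0.09 to +0.34 SD across 0%, 10% and 20% leavers. Under LOCF with leavers it is 0.00 to +0.24 SD. The BID PP population (Section 6.6) requires completion of Visit 4, so it behaves like the observed case.

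**TID at Day 120.** Over the same range of ρ, with Day 90 to Day 120 correlation 0.7, the mean is −0.17 to −0.56 SD if the dose change has no effect and −0.16 to +0.23 SD if it adds 0.4 SD. The direction is therefore not determined.

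**The case against.** The strongest reply is that nothing is misestimated. Section 5.1 labels each endpoint BID or TID, Section 8.0 calls the p-values exploratory, and measuring each patient at his own end of treatment is coherent. Rejecting zero in a BID group whose mean really is above zero is a correct rejection; it misleads only as a statement about all non-naïve patients. This stands.

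The size is also open to challenge. Titration follows the Day 90 symptom level, while the endpoint is a change from Day 0. If Day 0 and Day 90 satisfaction have equal SDs, and Day 0 satisfaction is independent of the Day 90 variables, then ρ = r/√2, where r is the Day 90 symptom–satisfaction correlation. A ρ of 0.7 would need r = 0.7 × √2 = 0.99. Other dependence structures could allow higher values of ρ, but 0.7 is best read as an extreme case.

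The undivided Visit 4 result is already planned in Section 9.3, and the TID Visit 4 row in Section 9.1, so a reader could assemble the picture. That is true, but no primary analysis combines them. The pooled ITT population of Section 6.4 does not either, since Section 9.1 applies it within dose groups.

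Finally, promoting an exploratory row in an open-label study whose conduct the SAP partly describes in the past tense carries a risk of selective emphasis. That calls for documented timing and does not remove the gap.

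**Conclusion.** The point holds as a mismatch between the primary objective and the population in which the primary endpoints are estimated; it should be fixed. For all non-naïve patients, the BID Day 90 change among observed patients tends to be too high by about +0.10 to +0.25 SD at ρ = 0.3 to 0.5, with upward rejection in about 9% to 33% of trials against 2.5%. This rests on the assumed N, titration share, absence of dropout, and worse symptoms going with lower satisfaction. At ρ = 0.1 rejection is only about 4% to 5%, so the shift is probably small for Convenience.

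A reader might infer more than the document supports:
- That the primary results are invalid. They are valid for their labelled groups.
- That false improvement of about 61% is to be expected. That needs ρ = 0.7 with a strict cut-off.
- That BID is always flattered. Under LOCF with dissatisfied leavers the shift can vanish or change sign.
- That the undivided Day 90 analysis is missing. It is planned, but only as exploratory.

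**What to change.** 1. Move the Visit 1 to Visit 4 TSQM change in all non-naïve patients, regardless of the dose assigned at Visit 4, from Section 9.3 into Sections 5.1 and 9.1 as a primary estimate, shown with and without LOCF. It removes selection by titration but not dropout bias, so both versions are needed.
2. Keep the BID (Day 90) and TID (Day 120) endpoints beside it and add: *These groups are defined by the Day 90 dose decision; their results are not estimates for all non-naïve patients.* They need not be demoted to descriptive status.
3. Set the ALL-patient qADAM endpoints (Section 5.2) and exploratory ALL-patient TSQM endpoints (Section 5.4) at Visit 4 instead of Visit 5. Sections 9.2 and 9.3 already plan those rows. For non-naïve TSQM this is the same quantity as in item 1 and need be listed only once.

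No new data or method is required. The cost is one more primary estimate per domain (from 2 × 3 = 6 to 3 × 3 = 9 for each population and missing-data approach, still unadjusted), and BID and TID lose sole primary prominence. The change, its rationale and its timing relative to data review should be documented as Section 1.0 requires for deviations, and aligned with the protocol, which was not available here.

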5.2 Secondary Efficacy Endpoints

The secondary efficacy endpoints are:

- change in satisfaction for each TSQM domain from Visit 2 (Day 30) to Visit 4 (Day 90) for naïve BID patients
- change in satisfaction for each TSQM domain from Visit 2 (Day 30) to Visit 5 (Day 120) for naïve TID patients
- change in total qADAM score from Visit 1 (Day 0) to Visit 4 (Day 90) for non-naïve BID patients
- change in total qADAM score from Visit 1 (Day 0) to Visit 5 (Day 120) for non-naïve TID patients
- change in total qADAM score from Visit 1 (Day 0) to Visit 4 (Day 90) for naïve BID patients
- change in total qADAM score from Visit 1 (Day 0) to Visit 5 (Day 120) for naïve TID patients
- change in total qADAM score from Visit 1 (Day 0) to Visit 5 (Day 120) for non-naïve ALL patients
- change in total qADAM score from Visit 1 (Day 0) to Visit 5 (Day 120) for naïve ALL patients
- change in total qADAM score from Visit 1 (Day 0) to Visit 5 (Day 120) for non-naïve and naïve ALL patients

- patient preference of therapy as measured by Part A of the Treatment Preference and Use Questionnaire at Visit 1 (Day 0) for the following groups of patients:
 - non-naïve and naïve ALL
 - non-naïve ALL
 - naïve ALL
 - non-naïve BID
 - naïve BID
 - non-naïve TID
 - naïve TID
- patient preference of therapy as measured by Part B of the Treatment Preference and Use Questionnaire for the following groups of non-naïve patients:
 - BID at Visit 4 (Day 90)
 - TID at Visit 4 (Day 90)
 - TID at Visit 5 (Day 120)
- patient preference of therapy as measured by Part C of the Treatment Preference and Use Questionnaire for the following groups of naïve patients:
 - BID at Visit 4 (Day 90)
 - TID at Visit 4 (Day 90)
 - TID at Visit 5 (Day 120)
- Natesto™ dosing frequency by hypogonadism treatment status (naïve/non-naïve) assigned at Visit 4 (Day 90)

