5.4 Exploratory Endpoints

Exploratory endpoints will include:

- change in satisfaction for each TSQM domain from Visit 1 (Day 0) to Visit 5 (Day 120) for non-naïve ALL patients
- change in satisfaction for each TSQM domain from Visit 2 (Day 30) to Visit 5 (Day 120) for naïve ALL patients

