6.4 Intent-to-Treat (ITT) Population

The ITT population includes all patients who are included in either the BID ITT or TID ITT population. Data will be analysed using the ITT population as per the Table Mock-Up (TMU) document.

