6.8 Per-Protocol (PP) Population

The PP population includes all patients who are included in either the BID PP or TID PP population. Data will be analysed using the PP population as per the Table Mock-Up (TMU) document.

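### Five endpoints for ALL patients are set at Visit 5, which only TID patients must attend: without LOCF they are TID-only, and with LOCF the handling of BID patients is not fixed

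*SAP*

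**What the plan says.** - **Endpoints.** SAP 5.2 sets three secondary qADAM endpoints at Visit 5 for the ALL group: non-naïve, naïve, and the two combined, the last worded as "change in total qADAM score from Visit 1 (Day 0) to Visit 5 (Day 120) for non-naïve and naïve ALL patients". SAP 5.4 adds two exploratory TSQM endpoints: "change in satisfaction for each TSQM domain from Visit 1 (Day 0) to Visit 5 (Day 120) for non-naïve ALL patients", and a matching one for naïve patients that starts at Visit 2.
- **Who is in ALL.** SAP 7.1: "The ALL treatment group will be defined as patients who were either naïve or non-naïve". Dosing frequency plays no part, so BID patients belong.
- **Populations.** The ALL qADAM analyses in 9.2 use ITT and PP. SAP 6.4: "The ITT population includes all patients who are included in either the BID ITT or TID ITT population". SAP 6.8: "The PP population includes all patients who are included in either the BID PP or TID PP population".
- **Who attends Visit 5.** Footnote b of the schedule in SAP 3.0: "Only patients assigned to NATESTO TID are required to complete Visit 5". The schedule shows Day 90 as end of study for BID patients and Day 120 for TID patients. Patients on BID "may have an increased daily dose adjustment on Day 90, based on their hypogonadism symptoms", and that decision creates the TID group.
- **Data handling.** SAP 7.2 uses data at the nominal visit where they were entered. SAP 7.3 imputes missing qADAM items and TSQM domain scores by LOCF in both the BID and TID groups, provided a Visit 2 value exists. SAP 9.2 and 9.3 require each ALL change analysis both with and without LOCF.

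**The concern.** The five endpoints name a population that includes BID patients and a visit that BID patients are not scheduled to attend. They are also the only endpoints in 5.2 and 5.4 meant to give a change in symptoms or satisfaction over BID and TID patients together.

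Followed literally, the plan could report a result headed ALL that describes only patients whose dosing was increased. Those patients were selected on hypogonadism symptoms, which is what the qADAM is used here to measure, so they cannot be assumed to represent the whole cohort. The LOCF version does not reliably correct this, because two programmers could follow 7.3 in good faith and produce results on different sets of patients.

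**Working it through.** The SAP gives no figure to reproduce: section 4.0 states that no formal sample size calculation is done, and no TID share, effect size or standard deviation appears. The check is a reading of the sections together, followed by head-count arithmetic.

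**Step 1: count.** Three qADAM endpoints (5.2) plus two TSQM endpoints (5.4) make 5. With three TSQM domains each, that is 3 + 2 × 3 = 9 tests per approach and population.

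**Step 2: without LOCF.** Visit 5 scores exist, per schedule, for TID patients only, and 7.2 has no rule that maps a Visit 4 score to Visit 5. Four of the five endpoints then repeat endpoints listed elsewhere:

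| ALL endpoint at Visit 5 | Becomes identical to |
|---|---|
| qADAM, non-naïve | qADAM, non-naïve TID (5.2) |
| qADAM, naïve | qADAM, naïve TID (5.2) |
| TSQM, non-naïve | TSQM, non-naïve TID, a primary endpoint (5.1) |
| TSQM, naïve | TSQM, naïve TID (5.2) |

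The fifth, combined qADAM, pools the two TID strata.

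**Step 3: with LOCF.** Section 7.3 does not say whether a visit that was never scheduled is missing, or up to which visit values are carried.
- If such a visit is not missing, the LOCF results are TID-only as well.
- If it is missing, BID scores from Day 90 or earlier are reported as Day 120, and the LOCF and no-LOCF versions of one endpoint cover different patients.

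The mention of both dosing groups in 7.3 may favour carrying forward. The BID efficacy analyses in 9.1 and 9.2, which stop at Visit 4, fit the other reading equally well.

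**Step 4: size.** Inputs: N = 100 (4.0, approximate) and TID share p = 0.2, 0.3, 0.4 (assumption). Let T be the TID mean change at Visit 5 and B the BID mean change at Visit 4, with complete data.
- No-LOCF ALL result: T, from Np patients.
- Change to each patient's last scheduled treatment visit: pT + (1 − p)B.
- Difference: T − [pT + (1 − p)B] = (1 − p)(T − B).

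| p | Patients used, Np | BID patients omitted, N(1 − p) | Difference |
|---|---|---|---|
| 0.2 | 20 | 80 | 0.8 (T − B) |
| 0.3 | 30 | 70 | 0.7 (T − B) |
| 0.4 | 40 | 60 | 0.6 (T − B) |

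For illustration only, take B = 6 and T = 2, which are not trial values. The no-LOCF ALL mean is 2.0. The mean with BID values carried forward is 0.2 × 2 + 0.8 × 6 = 5.2 at p = 0.2, 4.8 at p = 0.3 and 4.4 at p = 0.4.

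If LOCF does fill Visit 5 and data are complete, the ALL result is pT + (1 − p)B. The numerical difference from the last-scheduled-visit result is then 0, and the fault is the Day 120 label on 60 to 80 BID scores.

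**The case against.** The strongest reply is that the SAP can be read coherently: section 7.3 applies LOCF to both dosing groups, and carrying BID values forward is the only reading under which an ALL result at Visit 5 contains all patients. On that reading, with complete data, the LOCF number is the one wanted. In addition:
- The Table Mock-Up named in 8.0 is not available here and may settle the handling.
- ALL change at Visit 4 is already tabulated under 9.2 and 9.3, so no result is lost.
- Section 8.0 requires numbers of observations and missing observations, so a fall in n would be visible.
- The endpoints are secondary or exploratory, and p-values are presented as exploratory.
- The 20% to 40% share is assumed, and T − B is unknown.

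Most of this stands as a limit on weight. It does not repair the no-LOCF results, which are TID-only under any reading of 7.3. Nor does it repair the labelling: carrying forward still presents BID scores from Day 90 or earlier as Day 120. An endpoint's time point and its missing-data rule belong in sections 5 and 7.3, even if table shells illustrate them. The count of missing observations helps less than it seems to, because the SAP does not say whether BID patients count as missing at Visit 5.

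One section points the other way: 10.3 lists testosterone at Visit 5 for the BID groups. That is not an efficacy score, and it conflicts with the schedule in 3.0.

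**Conclusion.** The concern holds and should be fixed. Without LOCF, the five ALL endpoints are TID-only under the SAP's own schedule. With LOCF, they are either TID-only or mislabelled in time, and the text does not decide which.

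Under the assumed TID share of 20% to 40% of 100 patients with complete data, the combined qADAM result without LOCF leaves out 60 to 80 patients. It differs from the change to each patient's last scheduled treatment visit by 60% to 80% of the TID-minus-BID difference in mean change. The size of that difference cannot be judged from the SAP, so whether any conclusion would change is unknown. The head-counts apply to the combined endpoint only; the other four use naïve or non-naïve subsets whose sizes are not stated.

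The primary endpoints and the separate BID and TID endpoints are not affected.

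**What to change.** 1. In 5.2 and 5.4, redefine the five ALL endpoints as change to each patient's last scheduled treatment visit (Visit 4 for BID, Visit 5 for TID), and label them so. This still pools Day 90 and Day 120 scores, but says so openly. Avoid the term end of treatment: 7.1 ties it to the day on which "the last dose of treatment is taken. This date was not collected for this study".
2. Name the ALL change to Visit 4, already tabulated, as the result at a common time point.
3. State in 7.3 that LOCF does not fill visits a patient is not scheduled to attend, and that such visits are not counted as missing.
4. Label any ALL rows kept at Visit 5 as TID patients only.
5. Record the endpoint change and its reason in the SAP. If it is made after the plan is final, report it in the clinical study report as a deviation, as section 1.0 requires.

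The cost is low: SAP wording and table shells, with no new data. Two cautions apply. The protocol, not available here, should be checked in case it also sets Day 120 for all patients. Parts of the SAP are in the past tense, so data collection may already be advanced; the record should therefore state that the change follows from the visit schedule and not from results.
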